**7. Risks and Discomforts:**

Potential discomforts in this study could arise from the medications administered in this study, the repeated venipuncture (i.e., bruising or pain at site of needle entry), the completion of rating scales, and the behavioral and endocrine challenge studies.

Medications: We do not expect any adverse side effects associated with the hormonal manipulations outlined in this protocol for the following reasons: First, we will be administering the physiologically relevant steroid hormones (estradiol and progesterone) and not the substituted steroids (such as ethinyl estradiol or norethindrone) present in many oral contraceptives and which have been reported to have a potentially more serious profile of side

effects. Second, the doses of Lupron, estradiol and progesterone, and the duration for which they will be administered in this protocol, will result in plasma hormone levels comparable to those commonly used for in vitro fertilization (IVF) protocols lasting 1-3 months. Therefore, based on current IVF procedures (80 ,94-96) ([name], personal communication) we do not anticipate any adverse incidents arising from the proposed doses of estradiol and progesterone. Third, no adverse reactions or events were encountered in the 25 women who completed the study to date. Finally, comparable extended, uninterrupted gonadal steroid treatment (such as oral contraceptives) for 6 to 12 weeks has been shown to be well-tolerated (97).

Lupron: The most frequent adverse effect of Lupron is hot flushes (flashes) reportedly occurring in 4-89% of patients receiving the drug. Lupron-induced hot flushes have ranged in severity from occasional mild flushing to frequent sweating. Episodes of flushing appear to decrease with continued therapy in most patients receiving Lupron; however, in at least one study, the incidence of hot flushes did not appear to decrease with continued therapy. In a recently completed study of 400 women of reproductive age with either uterine fibroids or endometriosis who each received 3.75 mgs depot Lupron every month for a period of six months, the most common side effects reported to occur were as follows: 1) hot flashes of mild to moderate intensity (89%), 2) headache (22%), 3) nervousness or irritability (11%), and 4) insomnia (10%). Local irritation at the injection site was complained of in less than 10% of the patients in this sample, and there was a mean decrease in bone density, as measured by bone densitometry, of 3.4 to 4.0%, which totally reversed after the medication had been discontinued for six months. Approximately ten patients of the original sample of 400 found the side effects to be severe enough to discontinue therapy. In the majority of women regular menstrual cycle function returned within two months following the last injection of depot Lupron (Tapp Pharmaceuticals, personal communication). Blurred vision, myalgias, lethargy, memory

disorder, and numbness have been reported in less than 3% of patients receiving the drug. Thrombophlebitis, pulmonary embolus, and congestive heart failure have occurred rarely in patients receiving Lupron, but a causal relationship to the drug has not been established. Adverse GI effects occurring in 2% or more of patients receiving Lupron include nausea and/or vomiting, constipation, and anorexia. Diarrhea and a sour or unusual taste in the mouth have been reported less frequently. Other adverse effects of Lupron occurring in less than 3% of patients include decreased hematocrit and hemoglobin concentration, fatigue, fever, facial swelling, rash, hives, hair loss, and itching. From our experiences with 20 PMS patients and 20 controls, Lupron is well tolerated (no dropouts) with the most common side effects being hot flushes and a decrease in libido. Limited information is available on the acute toxicity of Lupron. Following subcutaneous administration of Lupron in rats at dosages 250-500 times the usual human dosage, dyspnea, decreased activity, and local irritation at the injection site were observed; however, there is no evidence to date that overdosage in humans produces similar adverse effects. Lupron dosages up to 20 mg daily for up to two years have not produced unusual adverse effects in humans. There has been one report of an anaphylactic reaction in a patient following administration of a GnRH agonist. Recent longitudinal follow-up studies of girls and boys receiving GnRH agonists as a treatment for precocious puberty report the development of normal reproductive function, skeletal growth, and fertility (98,99).

Estradiol: Nausea is the most common side effect of estrogen administration. At conventional replacement doses, higher than those employed in this protocol, this complaint seldom interferes with eating, and no weight loss has been reported. Breast engorgement, endometrial hyperplasia and bleeding are also common side effects of estrogen administration. Pre-existing fibroid tumors of the uterus may enlarge under the effects of estrogen; however, at the dosage and for the duration of estrogen administration in this protocol this risk is small.

The relationship between estrogen, both endogenous and exogenous, and the development of endometrial carcinoma has been suggested by several different lines of investigation (100). Numerous retrospective case control studies published since 1975 have indicated that post-menopausal exposure to unopposed estrogens for more than one year results in a two to 12 fold increased relative risk for endometrial cancer. A relationship between the dose and duration of estrogen use and the risk for endometrial cancer has also been shown, the risk being increased after one to four years of estrogen use and rising also with the dosage employed. However, the addition of progesterone to estrogen replacement therapy appears to decrease the risk of endometrial hyperplasia and endometrial cancer to equal or below that of women receiving no hormonal treatment. Recent studies suggest that the optimal regimen to prevent hyperplasia during long term ERT and thus, inferentially, the risk of carcinoma, consists of 12 to 13 days of progesterone treatment each month when estrogens are administered (101). There is an increase in thromboembolism in women receiving non-contraceptive estrogen therapy (102-106). Additionally, some but not all studies report an increase in risk of stroke (107,108) in older women taking estrogen therapy. However, these complications are unlikely at the dose and duration of estrogen replacement employed in this protocol, and in the younger age group of women who participate in this study. One study (94) reported no effect of the estrogen patch on the four clotting indices previously shown to be altered by oral contraceptive use (101,109,110). Blood pressure, on average, appears to be unaffected by estrogen therapy, although both increases and decreases have been reported. In observational studies, post-menopausal estrogen therapy has been observed to lower the relative risk of cardiovascular disease in some but not all studies (107,111). In contrast, recent randomized controlled trials in older postmenopausal women (e.g., Women's Health Initiative [WHI]) report an increased risk of cardiovascular disease (112). Emerging data suggest that these disparities in findings may be

related to the timing of initiation of estrogen therapy in relation to the proximity of menopause. Subgroup analyses of the combined estrogen and progestin (EPT) arm of the WHI demonstrated a significant interaction between coronary heart disease (CHD) risk and time since initiation of EPT, with an increased risk in the early years following initiation and a decreased risk in later years. Additionally, the increased risk of CHD was observed in older but not younger perimenopausal women (113-118). High doses of oral estrogens have been reported to elevate hepatocellular enzyme levels and, less commonly, cause cholestatic jaundice. The risk for gall stones and hepatocellular adenomas has been reported to be increased in association with oral contraceptive use, and although uncommon these complications may also occur with the use of replacement doses of estrogen (119,120). Estrogen therapy also may increase the risk of urinary incontinence in older postmenopausal women (121-123). Further, most studies have suggested an increased relative risk of breast cancer after four or five years' use (124-136), similar to the risk expected if the onset of menopause was delayed for a comparable length of time.

Due to the publicity surrounding the cancellation of the treatment arm of the Women's Health Initiative study (137) that involved the administration of combined conjugated estrogens and medroxyprogesterone acetate (Prempro), we have included the following statement in the consent documents:

Adverse Events Related to Combined Hormone Replacement and the Results of the Women's Health Initiative (WHI):

The WHI study demonstrated that continuous administration of one form of estrogen (conjugated estrogens) in combination with one form of progesterone (medroxyprogesterone acetate) is associated with an increased risk of dementia, heart attacks, stroke, blood clots, and breast cancer. Estradiol, the form of estrogen that we use in this study, is administered as a sole agent (with the exception of one week's combination with progesterone) and, consequently, we

do not expect that it will pose the increased risks observed with the chronic combination of the conjugated estrogens and medroxyprogesterone administered in the WHI study. Indeed, while the estrogen alone arm of the WHI trial was shown to be associated with an increased risk of stroke, no increased risk of either heart disease or breast cancer was observed (137,138).

Estrogens may precipitate migraine headaches, and depression has also been reported to occur with the use of estrogens. In general, considering the dose and duration of treatment that we propose to use in this protocol, the risk of developing such side effects is negligible.

Progesterone: Progesterone and the synthetic progestins are widely prescribed, with indications including dysfunctional uterine bleeding, endometriosis, mastodynia, galactorrhea, and precocious puberty (139). Side effects reported in women taking progestins may include breakthrough bleeding, edema, change in weight (increase or decrease), cholestatic jaundice, rash (with or without pruritus), depression, easy fatigue and sedation, lack of initiative, and chloasma. Since progestins are often used in women with antecedent menstrual irregularity, it is not clear whether the breakthrough bleeding represents an effect of the medication or refractoriness to treatment. In the large majority of patients, menstruation occurs predictably following withdrawal of progestins and is usually more regular than in spontaneous cycles. In a recent study, an average dose of 1750 mg of oral micronized progesterone was given to 59 women with PMS for a period of three months and was well tolerated by this sample. The side effects reported on progesterone were lightheadedness, fatigue, forgetfulness, and headaches. These were very mild and caused no dropouts ([name], personal communication).

For the sake of completeness we will also describe the side effects reported when estradiol and progesterone are combined in the form of oral contraceptives. Side effects observed in patients receiving combined oral contraceptives include nausea, breast soreness,

vaginal discharge, fluid retention, hypertension, and clotting abnormalities that have been associated with the estradiol component of the oral contraceptive. Thromboembolic disorders including thrombophlebitis, pulmonary embolism, and cerebral and coronary thrombosis appear to occur with greater frequency in women taking oral contraceptives. While the increased incidence of these disorders has been associated with the estradiol component of the oral contraceptives, it is now believed that the progestogen component may, to a lesser extent, contribute to the increased risk. There are relatively few reports associating oral contraceptives with the development of carcinomas (vaginal, uterine, hepatic, and mammary) despite the vast use of these agents, although this may reflect the latent period needed for cellular transformation. Finally, several reports suggest an association between intrauterine exposure to female sex hormones and congenital anomalies.

Any patient experiencing clinically significant side effects such as nausea, hypertension, vomiting or extreme fluid retention from the medication will have the dose titrated to achieve relief of the symptoms. If adequate relief cannot be achieved in this manner, drug treatment will be discontinued. Similarly if menopausal-like symptoms occurring secondary to GnRH agonist treatment are intolerable, drug treatment will be discontinued.

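### The WHI risk statement says estradiol is given alone except for one week with progesterone, but the schedule gives both hormones together for all 8 or 12 weeks of addback

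*Combined protocol and SAP*

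**What the plan says.** In section 7 (Risks and Discomforts, under Estradiol), the protocol refers to publicity about the stopped WHI combined-hormone arm and says "we have included the following statement in the consent documents". The statement that follows does three things.

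- It lists five harms found with the WHI combination: breast cancer, blood clots, stroke, heart attack and dementia.
- It describes this study's regimen: "Estradiol, the form of estrogen that we use in this study, is administered as a sole agent", "with the exception of one week" in combination with progesterone. Joined by the word *consequently*, it says the investigators "do not expect that it will pose the increased risks observed with the chronic combination" of the WHI compounds.
- It supports this with the estrogen-alone arm: "the estrogen alone arm of the WHI trial was shown to be associated with an increased risk of stroke", but "no increased risk of either heart disease or breast cancer was observed".

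Section 4(d) (Study Procedures, Research Procedures) sets out the regimen. After two months of Lupron with placebo versions of both hormones, active estradiol and progesterone are started. Both groups begin on estradiol 2 mg twice daily with progesterone 200 mg twice daily. The withdrawal group takes the pair for 8 weeks and the continued replacement group for 12. Doses are then titrated to blood levels, and a target progesterone-to-estradiol ratio is held so that estradiol does not act unopposed.

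**The concern.** The statement draws its conclusion from a fact about exposure: almost no time on both hormones together. If that fact is wrong, the inference goes with it. So does the comparison with the estrogen-alone arm, which is relevant only to women taking estrogen without a progestogen.

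What is at stake is the accuracy of risk disclosure. This is a mechanistic study that gives supraphysiologic hormone levels to women who are currently well, including controls with no psychiatric history. The protocol says these women are given this reason for not expecting five serious harms, and the reason describes a regimen that nobody is scheduled to take.

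**Working it through.** No statistical formula applies. The check sets the exposure in the statement against the schedule.

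**Inputs**

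- Combined exposure claimed: 1 week, estradiol otherwise alone (section 7, WHI statement).
- Combined exposure scheduled: 8 weeks or 12 weeks (section 4(d), Groups 1 and 2).
- Starting doses in both groups: estradiol 2 mg and progesterone 200 mg, each twice daily (section 4(d)).

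**Step 1: go through the schedule phase by phase, looking for estradiol alone.**

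| Phase | Withdrawal group | Continued replacement group |
|---|---|---|
| Lupron months 1–2 | placebo for both hormones | placebo for both hormones |
| Lupron months 3–4 | both active | both active |
| Lupron month 5 | placebo for both | both active |
| Two-month follow-up | unmedicated | unmedicated |

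Planned estradiol-only weeks: 0 in each group. No other section describes an estradiol-only phase or a one-week progesterone course. The Precis and section 1(c) also describe the two hormones as given together.

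**Step 2: starting daily doses.** Estradiol 2 × 2 mg = 4 mg; progesterone 2 × 200 mg = 400 mg. They begin at the same point in both groups.

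**Step 3: try to reproduce the stated one week.**

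- Stated: 1 × 7 = 7 days combined.
- Withdrawal group: 8 × 7 = 56 days, which is 8 − 1 = 7 weeks more than stated.
- Continued replacement group: 12 × 7 = 84 days, which is 12 − 1 = 11 weeks more than stated.

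The one-week figure cannot be reproduced for either group.

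**Step 4: follow the inference.** The word *consequently* comes straight after the sole-agent clause, so that clause is the stated premise, and it is false under the schedule. The sentence on the estrogen-alone arm assumes the same premise. Section 4(d) also runs against it directly: the hormone ratio is held precisely so that estradiol is not unopposed.

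The day counts are planned exposure. Section 8 allows hormones to be restarted if severe mood symptoms occur during withdrawal, so a woman in the withdrawal group could exceed 56 days.

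**The case against.** The strongest reply is that the damage is small. The statement names all five WHI harms before the disputed clause, so none is concealed. It limits its conclusion to long-term use of conjugated estrogens with medroxyprogesterone, and both distinctions, compound and duration, remain true of this regimen. Elsewhere section 7 describes the clotting risks of combined oral contraceptives, including a progestogen contribution. Section 3(c) excludes smokers and women with earlier clots, stroke, heart disease or breast cancer. All of this stands. It lowers the practical risk and keeps the point modest, but it does not make the sole-agent sentence true.

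Dose titration is a further reply. Doses can be changed for blood levels (section 4(d)) or side effects (section 7), and neither section says the two hormones must be reduced or stopped together. That is a reason to write *planned* rather than *always* in the correction. It does not create a sole-agent regimen.

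A reader might also infer more than the documents support:

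- *That women were misled or consent was defective.* The consent pages are not in the review copy. The forms may describe the regimen correctly beside this statement, or may no longer carry it.
- *That the regimen is unsafe, or that risk rises in proportion to the extra weeks.* The figures above are exposure times. The documents give no risk figure for 8 or 12 weeks of use.
- *That the statement implies 7 or 11 weeks of estradiol alone.* It gives no total duration, so no such figure or share can be derived from it.

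**Conclusion.** The point holds as an error in current risk text. The WHI statement misdescribes the regimen: 7 days of combined exposure stated, 56 or 84 days planned, and no planned time on estradiol alone in either group. Its stated reason and its appeal to the estrogen-alone arm therefore do not apply to the regimen as scheduled.

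This rests on reading *consequently* as attached to the sole-agent clause, which is the natural reading, and on the dosing schedule in section 4(d) as written. A low-risk expectation may still be defensible on other grounds; this point neither tests nor disputes them. The error is certain in the protocol text. Its effect on what participants understood cannot be judged. It should be corrected because it sits in text meant for participants, but it leaves the regimen, randomisation, endpoints and analysis unaffected.

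**What to change.** In the WHI statement in section 7, and in any matching consent text:

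1. Replace the sole-agent clause, including the one-week exception, with wording such as: *estradiol and progesterone are given together throughout the hormone phase of this study; no period on estradiol alone is planned*. This gives no durations, so it does not reveal the timing of the switches. Section 4(d) tells women only that placebo will change to active medication at some point.
2. Delete *consequently*, and stop using the estrogen-alone arm as reassurance.
3. Keep all five listed harms. Stroke stays because it is on the combined-therapy list, whatever happens to the estrogen-alone sentence.
4. Rest any low-risk expectation only on general grounds the protocol already states: dose, short duration, younger age and different compounds. Do not assign a ground to each harm, because the protocol does not supply one for every harm; dementia, for example, appears only in the WHI statement. Heart disease needs particular care. Section 7 reports the combined-arm excess "with an increased risk in the early years following initiation", so short duration alone is not a clean reassurance. It also says "the increased risk of CHD was observed in older but not younger perimenopausal women", but section 3(c) excludes perimenopausal women, so that finding should not be presented as direct evidence for this sample.

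The cost is an amendment to one protocol paragraph, a check of the consent form with the same edit where needed, and notice to enrolled women if the IRB asks for it. No change to treatment is proposed.

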#### Venipuncture:

One discomfort of this study may occur due to the venipuncture and multiple blood sampling. The total blood withdrawal is estimated to be 50 ml per clinic visit for a total of 750 ml for the 28 week study (i.e., 15 visits). An additional 60 ml sample of blood will be obtained for genetics (50ml) and IPCs (10ml) that will be timed to coincide with one of the regular visits in those women currently participating in this protocol. Total blood withdrawal over 28 weeks of study duration - 1,080 ml) and falls within NIH guidelines

(550 ml per eight week period). The total blood volume collected will be 200 ml every eight weeks (4 visits= 200 ml = 200 ml) plus one 10 mL additional sample for IPCs and one 50 ml sample for genetics.

#### Psychological and Cognitive tests:

The risks and discomforts of the symptom evaluations and baseline exams are minimal. No discomfort is expected to be associated with the physical examination or the clinical interview other than potential stress of answering personal questions. All clinical assessors have extensive experience in clinical psychiatric assessment and will make every effort to implement protocol procedures in a sensitive and supportive manner. Research interviews will be interrupted if subjects become distressed or object to answering questions. Other measures to minimize risks include the careful assessment of each subject before the study, and close clinical scrutiny during all aspects of the study.

Intravenous catheter insertion may be momentarily painful and there is a slight risk of infection or inflammation at the site of the catheter insertion. Some people faint when needles are inserted, so this procedure will be performed with the subject seated.

**History and Physical Exam and Laboratory Tests:** It is possible that during the evaluation portion of the study a subject may be found to have a medical problem of which they were previously unaware. In that event, the participant will be given the results and an appropriate referral made as indicated by the condition identified.

#### Donation of blood for genetic material:

Under some circumstances, it can be a risk for genetic information about an individual to be known. Variation in some genes is known to be directly related to risk for certain illnesses. Other genes may be shown at some point in the future to be related to illness. Since the results of these genetic tests may allow prediction of risk of illness in some cases, it is possible this

information could be used against a subject participating in the study. Although there are no physical risks associated with participation in genetic studies, apart from those routinely associated with phlebotomy, psychological and social/economic risks associated with genetics studies of the kind described here are difficult to define, and remain the subject of heated controversy in the ethics community. The major risk, to the degree that any exists, is that a breach of confidentiality regarding genetic studies that resulted in third parties finding out genetic information about a person could theoretically place a person at risk for loss of insurance, loss of employment, etc. because of genotype-based discrimination. To our knowledge, no person has ever suffered harm for the reasons just described as a result of participating in a genetics research study. Regardless, our written informed consent process will go over these risks carefully. In addition, subjects will have the right to “withdraw” from the research by having their DNA sample destroyed. Finally, all research records containing any subject-identifying information will be stored under lock and key, or in secured computing environments by the CTDB. Personal identifiers are never associated directly with genotypes in the same data file - all genotype information is indexed only to de-identified subject codes. With these safeguards in place, we are confident the research is virtually without psycho-social-economic risk to subjects.

